12.0 DATA COLLECTION AND MONITORING

All data collection will be done using the REDCAP database. Only those involved in data collection and analysis who are included on the IRB will have access to the data.

13.0 STATISTICAL CONSIDERATIONS

13.1 The goal of this study is to evaluate the feasibility, safety, and efficacy of acamprosate for management of AUD in post-liver transplant patients. All patients will be post-LT with a pre-LT diagnosis of ALD. As our usual number of transplants per year is 120 and 30% of patients have ALD (includes AH) as a diagnosis, we do not anticipate any difficulties in identifying 30 participants for this study. Feasibility will be assessed via completion rates, number of missed doses per patient, and number of patients who completed 3 monthly refills for the study. Safety will be measured via % total, minor, moderate, and major side-effects documented via the GASE survey. Finally, efficacy will be measured via % maintained abstinence, reduction in alcohol cravings determined via PACS score, % of alcohol relapses determined via TLFB survey, PEth, and self-reporting and patient and graft survival in our patients transplanted for ALD. Demographic variables will be compared between SOC and acamprosate+SOC groups using descriptive statistics. Efficacy and safety outcomes will be compared to control group using wilcoxan pair rank sum. Cox regression analysis will be done to determine determinants of alcohol relapse and graft failure in both SOC and SOC+acamprosate

group. Finally, time to relapse will be measured in both SOC and SOC+acamprosate group via Kaplan meier plots.

13.2 Given the small number of patients (30), we will not perform a stratified randomization based upon age, race, ethnicity and timing from transplant but rather compare frequencies of different ethnicities in our descriptive statistics section.

14.0 REGISTRATION GUIDELINE

- 14.1 Patients will be contacted by our research coordinator. Patients will be randomized in a 2:1 fashion and stratified based upon sex.
- 14.2 Patients will undergo an intake session where an informed consent and HIPPA release form will be signed. All patients will receive a signed and dated copy of the Informed Consent Form once enrolled.

15.0 BIOHAZARD COMTAINMENT

No biohazard materials will be produced during this study, hus containment protocol is not applicable.

16.0 ETHICAL AND REGULATORY CONSIDERATIONS

All institutional and Federal regulations concerning the Informed Consent form will be fulfilled. The study will be conducted in adherence to ICH Good Clinical Practice.

Appendix I: informed consent and HIPAA form

Appendix II: Questionnaires &/or Survey Forms (if applicable)

₹EDCap°

GASE & PACS Week 1

Please complete the survey below.

Thank you!

GASE Survey				
Please rate whether you experienced one of the following complaints during the last seven days by using the scale below. Please indicate by selecting yes or no whether you believe that these symptoms are related to your current medication				
0 = Complaint not present 1 = Mild: complaint causes mild distress or discomfort, but no impairment in daily functioning 2 = Moderate: complaint causes moderate distress or discomfort or at least some impairment in daily functioning 3 = Severe: complaint causes severe distress and discomfort, severe impairment in daily functioning, or acute danger to health Please try to choose an answer even if you are not completely sure.				
In the last seven days I had the followi	O O 1 O 2 O 3 (Intensity)			
Is this complaint related to your current medication?	○ Yes ○ No			
Hair Loss	○ 0 ○ 1 ○ 2 ○ 3 (Intensity)			
Is this complaint related to your current medication?	○ Yes ○ No			
Dry Mouth	○ 0 ○ 1 ○ 2 ○ 3 (Intensity)			
Is this complaint related to your current medication?	○ Yes ○ No			

Dizziness	\bigcirc 0 \bigcirc 1 \bigcirc 2 \bigcirc 3 (Intensity)
Is this complaint related to your current medication?	○ Yes ○ No
Chest Pain	○ 0 ○ 1 ○ 2 ○ 3 (Intensity)
Is this complaint related to your current medication?	○ Yes ○ No
Palpitations, irregular heartbeat	○ 0 ○ 1 ○ 2 ○ 3 (Intensity)
Is this complaint related to your current medication?	○ Yes ○ No
Breathing Problems	○ 0 ○ 1 ○ 2 ○ 3 (Intensity)
Is this complaint related to your current medication?	○ Yes ○ No
Low blood pressure, other circulation problems	○ 0 ○ 1 ○ 2 ○ 3 (Intensity)
Is this complaint related to your current medication?	○ Yes ○ No
Abdominal Pain	○ 0 ○ 1 ○ 2 ○ 3 (Intensity)
Is this complaint related to your current medication?	○ Yes ○ No
Nausea	○ 0 ○ 1 ○ 2 ○ 3 (Intensity)
Is this complaint related to your current medication?	○ Yes ○ No
Vomiting	○ 0 ○ 1 ○ 2 ○ 3 (Intensity)
Is this complaint related to your current medication?	○ Yes ○ No
Constipation	○ 0 ○ 1 ○ 2 ○ 3 (Intensity)
Is this complaint related to your current medication?	○ Yes ○ No

Diarrhea	○ 0 ○ 1 ○ 2 ○ 3 (Intensity)
Is this complaint related to your current medication?	○ Yes ○ No
Reduced Appetitie	○ 0 ○ 1 ○ 2 ○ 3 (Intensity)
Is this complaint related to your current medication?	○ Yes ○ No
Increased Appetite	○ 0 ○ 1 ○ 2 ○ 3 (Intensity)
Is this complaint related to your current medication?	○ Yes ○ No
Difficulty Urinating	○ 0 ○ 1 ○ 2 ○ 3 (Intensity)
Is this complaint related to your current medication?	○ Yes ○ No
Problems with sexual performance or sex organs	○ 0 ○ 1 ○ 2 ○ 3 (Intensity)
Is this complaint related to your current medication?	○ Yes ○ No
Females: Painful or irregular menstruation	○ 0 ○ 1 ○ 2 ○ 3 (Intensity)
Is this complaint related to your current medication?	○ Yes ○ No
0 = Complaint not present	
1 = Mild: complaint causes mild distress or discomfo	ort, but no impairment in daily functioning
2 = Moderate: complaint causes moderate distress of	or discomfort or at least some impairment
in daily	
functioning	
3 = Severe: complaint causes severe distress and di	scomfort, severe impairment in daily
functioning,	
or acute danger to health	
Skin Rash or Itching	\bigcirc 0 \bigcirc 1 \bigcirc 2 \bigcirc 3
Skill Rasil of itelling	(Intensity)
Is this complaint related to your current medication?	○ Yes ○ No

Tendency to develop bruises	○ 0 ○ 1 ○ 2 ○ 3 (Intensity)
Is this complaint related to your current medication?	○ Yes ○ No
Fever, increased temperature	○ 0 ○ 1 ○ 2 ○ 3 (Intensity)
Is this complaint related to your current medication?	○ Yes ○ No
Abnormal sweating	○ 0 ○ 1 ○ 2 ○ 3 (Intensity)
Is this complaint related to your current medication?	○ Yes ○ No
Hot flashes	○ 0 ○ 1 ○ 2 ○ 3 (Intensity)
Is this complaint related to your current medication?	○ Yes ○ No
Convulsions or seizures	○ 0 ○ 1 ○ 2 ○ 3 (Intensity)
Is this complaint related to your current medication?	○ Yes ○ No
Fatigue, loss of energy	○ 0 ○ 1 ○ 2 ○ 3 (Intensity)
Is this complaint related to your current medication?	○ Yes ○ No
Tremor	○ 0 ○ 1 ○ 2 ○ 3 (Intensity)
Is this complaint related to your current medication?	○ Yes ○ No
Insomnia, sleeping problems	○ 0 ○ 1 ○ 2 ○ 3 (Intensity)
Is this complaint related to your current medication?	○ Yes ○ No
Nightmares or abnormal dreams	○ 0 ○ 1 ○ 2 ○ 3 (Intensity)
Is this complaint related to your current medication?	○ Yes ○ No

Back pain	○ 0 ○ 1 ○ 2 ○ 3 (Intensity)
Is this complaint related to your current medication?	○ Yes ○ No
Muscle pain	○ 0 ○ 1 ○ 2 ○ 3 (Intensity)
Is this complaint related to your current medication?	○ Yes ○ No
Joint pain	○ 0 ○ 1 ○ 2 ○ 3 (Intensity)
Is this complaint related to your current medication?	○ Yes ○ No
Agitation	○ 0 ○ 1 ○ 2 ○ 3 (Intensity)
Is this complaint related to your current medication?	○ Yes ○ No
Irritability, nervousness	○ 0 ○ 1 ○ 2 ○ 3 (Intensity)
Is this complaint related to your current medication?	○ Yes ○ No
Depressed mood	○ 0 ○ 1 ○ 2 ○ 3 (Intensity)
Is this complaint related to your current medication?	○ Yes ○ No
Thoughts about suicide	○ 0 ○ 1 ○ 2 ○ 3 (Intensity)
Is this complaint related to your current medication?	○ Yes ○ No
Anxiety, Fearfulness	○ 0 ○ 1 ○ 2 ○ 3 (Intensity)
Is this complaint related to your current medication?	○ Yes ○ No

- 0 = Complaint not present
- 1 = Mild: complaint causes mild distress or discomfort, but no impairment in daily functioning
- 2 = Moderate: complaint causes moderate distress or discomfort or at least some impairment in daily

functioning

3 = Severe: complaint causes severe distress and discomfort, severe impairment in daily functioning,

or acute danger to health

Have you had any further symptoms?	○ Yes ○ No (Please name the symptom)	
How many additional symptoms have you had?	○ 1 ○ 2 ○ 3 ○ 4 (Intensity)	
What was the first symptom?		
	(Please name the symptom)	
What was the intensity of the first symptom? ([symptom1])	○ 0 ○ 1 ○ 2 ○ 3 (Intensity)	
Is this complaint related to your current medication?	○ Yes ○ No	
What was the second symptom?		
	(Please name the symptom)	
What was the intensity of the second symptom? ([symptom2])	○ 0 ○ 1 ○ 2 ○ 3 (Intensity)	
Is this complaint related to your current medication?	○ Yes ○ No	
What was the third symptom?		
	(Please name the symptom)	
What was the intensity of the third symptom? ([symptom3])	\bigcirc 0 \bigcirc 1 \bigcirc 2 \bigcirc 3 (Intensity)	
Is this complaint related to your current medication?	○ Yes ○ No	
Please list the additional symptom(s) you are		
experiencing and relay them to your study coordinator at the next study appointment	(Please name the symptom(s))	

Penn Alcohol Craving Scale (PACS) Please read each item carefully and circle the number that best describes your craving during the past week. 1. How often have you thought about drinking or about Never-0 times during this period of time Rarely-1 to 2 times during this period of time how good a drink would make you feel during this period? Occasionally-3 to 4 times during this period of time O Sometimes-5 to 10 times during this period of time Often-11 to 20 times during this period of time Most of the time-20 to 40 times during this period O Nearly all of the time-more than 40 times or more than 6 times per day 2. At its most severe point, how strong was your None at all. Slight, that is a very mild urge. craving during this period? Mild urge. Moderate urge. Strong urge, but easily controlled. Strong urge and difficult to control. O Strong urge and would have drunk alcohol if it were available. 3. How much time have you spent thinking about O None at all O Less than 20 minutes. drinking or about how good a drink would make you feel during this period? 21-45 minutes. 46-90 minutes. 90 minutes-3 hours. Between 3 and 6 hours. More than 6 hours. 4. How difficult would it have been to resist taking a Not difficult at all. O Very mildly difficult. drinking during this period of time if you had known a Mildly difficult. bottle were in your house? Moderately difficult. Very difficult. Extremely difficult. Would not be able to resist. 5. Keeping in mind your responses to the previous Never thought about drinking and never had the questions, please rate your overall average alcohol urge to drink. craving for the stated period of time. Rarely thought about drinking and rarely had the urge to drink. Occasionally thought about drinking & occasionally had the urge to drink. Sometimes thought about drinking & sometimes had the urae to drink. Often thought about drinking & often had the urge to drink. Thought about drinking most of the time & had the urae to drink Thought about drinking nearly all of the time & had the urge to drink

Timeline Followback Method Assessment	
Timeline followback Week Start Date	
Have you used any illicit substances or alcohol on Monday	○ Yes ○ No
Substances used on Monday	☐ Alcohol ☐ Cannabinoids/Marijuana ☐ Cocaine ☐ Crack ☐ Amphetamine-type stimulants ☐ Opiod Analgesics, including methadone ☐ heroin ☐ Hallucinogens, including MDMA/ecstasy ☐ sedatives and hypnotics, excluding benzodiazepin ☐ Benzodiazepines ☐ Inhalants ☐ other drugs
Since you said yes to alcohol, how many standard drinks did you drink. A standard drink is one 12-ounce bottle/can of regular beer, OR One 5-ounce glass of regular (12%) wine, OR 1 1/2 ounces of hard liquor either straight or in a mixed drink OR One 12-ounce wine cooler	
other drugs	
Have you used any illicit substances or alcohol on Tuesday	○ Yes ○ No
Substances used on Tuesday	☐ Alcohol ☐ Cannabinoids/Marijuana ☐ Cocaine ☐ Crack ☐ Amphetamine-type stimulants ☐ Opiod Analgesics, including methadone ☐ heroin ☐ Hallucinogens, including MDMA/ecstasy ☐ sedatives and hypnotics, excluding benzodiazepines ☐ Inhalants ☐ other drugs
Since you said yes to alcohol, how many standard drinks did you drink. A standard drink is one 12-ounce bottle/can of regular beer, OR One 5-ounce glass of regular (12%) wine, OR 1 1/2 ounces of hard liquor either straight or in a mixed drink OR One 12-ounce wine cooler	
other drug	
Have you used any illicit substances or alcohol on Wednesday	

	Substances used on Wednesday	□ Alcohol □ Cannabinoids/Marijuana □ Cocaine □ Crack □ Amphetamine-type stimulants □ Opiod Analgesics, including methadone □ heroin □ Hallucinogens, including MDMA/ecstasy □ sedatives and hypnotics, excluding benzodiazepine □ Benzodiazepines □ Inhalants □ other drugs
	Since you said yes to alcohol, how many standard drinks did you drink. A standard drink is one 12-ounce bottle/can of regular beer, OR One 5-ounce glass of regular (12%) wine, OR 1 1/2 ounces of hard liquor either straight or in a mixed drink OR One 12-ounce wine cooler	
	other drug	
4.	Have you used any illicit substances or alcohol on Thursday	○ Yes ○ No
	Substances used on Thursday	☐ Alcohol ☐ Cannabinoids/Marijuana ☐ Cocaine ☐ Crack ☐ Amphetamine-type stimulants ☐ Opiod Analgesics, including methadone ☐ heroin ☐ Hallucinogens, including MDMA/ecstasy ☐ sedatives and hypnotics, excluding benzodiazepine ☐ Benzodiazepines ☐ Inhalants ☐ other drugs
	Since you said yes to alcohol, how many standard drinks did you drink. A standard drink is one 12-ounce bottle/can of regular beer, OR One 5-ounce glass of regular (12%) wine, OR 1 1/2 ounces of hard liquor either straight or in a mixed drink OR One 12-ounce wine cooler	
	other drug	
5.	Have you used any illicit substances or alcohol on Friday	○ Yes ○ No

	Substances used on Friday	□ Alcohol □ Cannabinoids/Marijuana □ Cocaine □ Crack □ Amphetamine-type stimulants □ Opiod Analgesics, including methadone □ heroin □ Hallucinogens, including MDMA/ecstasy □ sedatives and hypnotics, excluding benzodiazepine □ Benzodiazepines □ Inhalants □ other drugs
	Since you said yes to alcohol, how many standard drinks did you drink. A standard drink is one 12-ounce bottle/can of regular beer, OR One 5-ounce glass of regular (12%) wine, OR 1 1/2 ounces of hard liquor either straight or in a mixed drink OR One 12-ounce wine cooler	
	other drug	
6.	Have you used any illicit substances or alcohol on Saturday	○ Yes ○ No
	Substances used on Saturday	☐ Alcohol ☐ Cannabinoids/Marijuana ☐ Cocaine ☐ Crack ☐ Amphetamine-type stimulants ☐ Opiod Analgesics, including methadone ☐ heroin ☐ Hallucinogens, including MDMA/ecstasy ☐ sedatives and hypnotics, excluding benzodiazepine ☐ Benzodiazepines ☐ Inhalants ☐ other drugs
	Since you said yes to alcohol, how many standard drinks did you drink. A standard drink is one 12-ounce bottle/can of regular beer, OR One 5-ounce glass of regular (12%) wine, OR 1 1/2 ounces of hard liquor either straight or in a mixed drink OR One 12-ounce wine cooler	
	other drug	
7	Have you used any illicit substances or alcohol on Sunday	○ Yes ○ No

Substances used on Sunday	☐ Alcohol ☐ Cannabinoids/Marijuana ☐ Cocaine ☐ Crack ☐ Amphetamine-type stimulants ☐ Opiod Analgesics, including methadone ☐ heroin ☐ Hallucinogens, including MDMA/ecstasy ☐ sedatives and hypnotics, excluding benzodiazepine ☐ Benzodiazepines ☐ Inhalants ☐ other drugs
Since you said yes to alcohol, how many standard drinks did you drink. A standard drink is one 12-ounce bottle/can of regular beer, OR One 5-ounce glass of regular (12%) wine, OR 1 1/2 ounces of hard liquor either straight or in a mixed drink OR One 12-ounce wine cooler other drug

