7.0 STUDY AGENT ADMINISTRATION OR INTERVENTION AND TOXICITY MANAGEMENT PLAN

7.1 Treatments

A. Standard of Care (SOC): Participants will be expected to complete a weekly telemedicine visit with a research member for at least 3 months, required to fill out weekly surveys (figure 2) (Penn Alcohol Craving Scale (PACS), Alcohol Timeline Followback (TLFB), and Generic Assessment of Side Effects in Clinical Trials (GASE) prior to these visits and expected to be compliant with acamprosate if randomized to that group.

B. SOC+ Acamprosate: Participants randomized to this arm will participate in SOC + take acamprosate 666 mg TID daily for three months.

7.21

AGENT	DOSE	ROUTE	DAYS	ReRx INTERVAL	NOTES
Acamprosate	666 mg	PO TID	Daily	4 weeks	maximum cumulative dose 500 mg/m ²

- 7.31 A patient may always be removed from treatment whenever he/she wishes
- 7.32 Treatment will be discontinued or held at discretion of investigators if patients experience any moderate-severe side effects as evaluated in section 8.0 thought to be secondary to acamprosate.

8.0 ASSESSMENT OF EFFICACY AND SAFETY

8.1 Acamprosate's package insert includes a comprehensive list of adverse events in over 7000 patients exposed to acamprosate¹⁴. However, adverse events are listed without regard to the causal relationship of the events to the drug¹⁴. Only diarrhea and flatulence appear to be significantly associated with acamprosate¹⁴. There is no evidence that acamprosate has additional risks in the liver transplant population⁸. Multiple meta analyses have found that the only side effect significantly associated with acamprosate over placebo is diarrhea^{8,15}. Flatulence is the only other adverse effect that has been significantly associated with acamprosate over placebo¹¹. In a review of clinical trials, diarrhea was observed in 10-17% of patients treated with acamprosate (versus 10-11% in placebo)^{11,12}. Diarrhea appears to be acamprosate dose dependent, settles within a few days, and mostly mild or moderate in severity¹¹. If diarrhea was severe, temporary dose reduction was beneficial⁸. Of note, no statistically significant differences were observed between groups (acamprosate versus placebo) in terms of premature withdrawals from treatment due to adverse effects¹². No clinically meaningful differences have been found comparing acamprosate and placebo regarding the incidence of clinically significant postbaseline abnormalities for any hematology

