- 8.11 Patients will undergo a self-administered weekly survey, Generic Assessment of Side Effects in Clinical Trials (GASE) to evaluate for potential side effects and toxicities. They will also undergo standard of care laboratory testing as well to check renal function and graft function along with immunosuppression levels. Details regarding the survey are listed in Appendix III.
- 8.12 There are no known long term drug toxicities associated with acamprosate. The recommended long-term dose for acamprosate is 666 mg TID PO daily unless the patient has severe renal impairment (CrCl of 30 mL/min or less) or levels hypersensitivity to acamprosate calcium or any of its components, in which case, acamprosate is contraindicated. If the patients choose to continue acamprosate after this study, they will continue to follow with their primary transplant hepatologist who can monitor for adverse side effects such as kidney dysfunction, hypersensitivity, diarrhea, and flatulence.
- 8.2 Complete discontinuation is advised if the patient experiences any drug toxicities related to acamprosate. Patients should not restart treatment if toxicity is thought to be related to acamprosate.
- 8.3
- 8.31 If a patient experiences an adverse event such as an unexpected or fatal toxicity, the event will be immediately (within 24 hours) reported to the primary medical care team so patient can receive the appropriate care.
- 8.32 We will then report the event to the IRB and FDA.

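### The weekly GASE form asks for diarrhea by name but, in every readable item, not for flatulence, the other effect the protocol links to acamprosate; a fourth written-in symptom has no grading fields.

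*Combined protocol and SAP*

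**What the plan says.** Section 8.1 states: "Only diarrhea and flatulence appear to be significantly associated with acamprosate". It repeats the point after discussing diarrhea: "Flatulence is the only other adverse effect that has been significantly associated with acamprosate over placebo". Section 8.12 tells the hepatologist of a patient who stays on the drug after the study what to look for: "monitor for adverse side effects such as kidney dysfunction, hypersensitivity, diarrhea, and flatulence".

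Section 13.1 defines the side-effect endpoint: "Safety will be measured via % total, minor, moderate, and major side-effects documented via the GASE survey". Section 10.0 uses the same definition and adds mortality. Section 8.11 makes GASE the weekly self-completed survey for side effects and toxicities, and section 3.0 and the study calendar in section 9.0 also have it collected weekly. Sections 10.0 and 13.1 compare safety between the two arms.

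The form in Appendix II lists complaints, each with a 0 to 3 intensity and a yes/no on relation to current medication. After the list it asks "Have you had any further symptoms" and then "How many additional symptoms have you had", with answers 1 to 4. The last further symptom with its own fields is introduced by "What was the third symptom". Anything beyond it is typed into a free-text box and passed on to the coordinator at the next appointment.

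**The concern.** The protocol says which effects it expects from the drug, and the instrument that measures safety should ask about them. It prompts every week for diarrhea, and for complaints such as hair loss and hot flashes that the protocol does not tie to acamprosate. It does not appear to prompt for flatulence.

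A symptom that patients must think of and type in is usually reported less often than one they only have to tick. If so, the flatulence rate from this pilot will be too low and will have been collected differently from the diarrhea rate. Feasibility and safety are the first goal in section 2.0, and such rates are what a later trial would draw on.

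The second matter is grading. The endpoint is split by severity, so a symptom with no intensity field has no obvious place in the minor, moderate and major percentages. Section 7.32 also refers to the severity of side effects when it speaks of holding or discontinuing treatment; that rule is not in question here.

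**Working it through.** The plan gives no figure to reproduce. The check is a count of the form's rows and fields, set against section 8.1.

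1. **Prompted rows, in form order.**
   - First row to reduced appetite: 14
   - Increased appetite to agitation: 18
   - Irritability to anxiety: 4
   - Total: 14 + 18 + 4 = 36

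2. **Readable labels.** The label of the first row is lost in the text reviewed; what stands there is the truncated lead-in "In the last seven days I had the followi". That leaves 36 − 1 = 35 readable labels.

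3. **Match to section 8.1.** Among the 35, diarrhea appears once; flatulence, gas or bloating appears 0 times.

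4. **Could the lost label be flatulence?** Abdominal pain, nausea, vomiting, constipation and diarrhea stand together further down the form. The lost row is away from that block, directly before hair loss. Flatulence there is unlikely but not excluded.

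5. **Write-in section.**

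| Further symptom | Can be declared | Intensity field | Relatedness field |
|---|---|---|---|
| First | yes | yes | yes |
| Second | yes | yes | yes |
| Third | yes | yes | yes |
| Fourth | yes | no | no |

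Declared minus graded: 4 − 3 = 1 symptom without a grade on the form.

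6. **Routes for flatulence.** If written in as the first, second or third further symptom, it is graded exactly like a listed item. If written in fourth, it is named in free text and relayed. If not written in, GASE does not record it. Section 3.0 has side effects and new symptoms passed to the hepatologist, but neither that section nor the form describes assigning a grade to what is relayed.

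**The case against.** The strongest reply is that GASE is a cited generic instrument and that a fixed list with an open section is a legitimate design. The patient is asked about further symptoms on the form and has three fully graded slots. No endpoint or analysis is specific to flatulence. Diarrhea, depressed mood and suicidal thoughts are all itemised. Section 8.1 itself reports meta-analyses in which diarrhea alone stood out, so the evidence on flatulence is less uniform. The mention in section 8.12 concerns care after the study, not what GASE should capture.

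Most of this stands, and it keeps the point small. It does not explain why one of two named drug effects should be left to recall while the other is prompted.

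Four stronger readings are tempting, and the documents do not support them:

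- **That flatulence will go ungraded.** That needs at least four unlisted symptoms in one week, with flatulence entered after the third.
- **That a fourth symptom cannot reach the endpoint.** The form has it relayed to the coordinator, both arms have weekly calls, and the overall percentage of side effects needs no grade. What is missing is a described grading step.
- **That a particular number of cases will be missed.** The protocol gives neither a flatulence rate nor a rate at which patients volunteer symptoms; its 10–17% is for diarrhea. Weekly completion over a 14-week study part gives repeated chances of capture.
- **That the comparison between arms is biased in a known direction.** The form is the same for both arms. Open-label expectation can affect every self-rated item, including diarrhea, and a named flatulence item would not remove it.

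**Conclusion.** The point holds as a minor gap between the protocol's safety background and its safety form. Of 35 readable prompted items, one names diarrhea and none names flatulence. The recorded flatulence rate is therefore likely to be too low and not comparable with the diarrhea rate. Secondarily, one of the four further symptoms a patient may declare has no intensity or relatedness field and may drop out of the severity percentages.

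This rests on four assumptions: the unreadable first label is not flatulence; the form shown for week 1 is used in every week; the free-text box is meant for symptoms beyond the third; and patients report an unnamed symptom less often than a named one. The last is general experience, not something the documents quantify, so no size is attached to the under-recording. No planned conclusion is shown to change.

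**What to change.** First check the label of the opening row on the original form. If it is not flatulence:

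- Add one flatulence item to the weekly REDCap form, worded identically for both arms and placed after the standard GASE items, with the same 0 to 3 intensity and relatedness question.
- Give the fourth further symptom the intensity and relatedness fields that the first three have.
- State in section 13.1 that the added item is reported on its own line, apart from the standard GASE percentages.

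The cost is a small REDCap edit and one more question per week, with no change to visits, sample size or treatment. The one drawback is that the added item is not part of the standard GASE, hence the separate reporting. If some patients have already completed weeks on the present form, record the date of the change, because flatulence reports before and after it will not be comparable.
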